5. INCLUSION

Inclusion criteria:

 \geq 60 yrs; having cardiac surgery at Strong Memorial Hospital; can provide consent; able to speak, read, and write English (as the instruments, including semi-structured interviews, used in this protocol have been validated in English); family member or close friend for collateral.

Exclusion criteria:

Exclusion criteria with rationales are described in **Table 4**. Subjects will be screened in person or by phone for eligibility.

Table 4 - Exclusion criteria with explanation				
Exclusion criteria	Definition (rationale)			
Prior cardiotomy	Per self-report or chart (sequelae of prior surgery)			
Infectious endocarditis	Per chart (potential septic emboli)			
Emergency surgery	Per chart (baseline eval impossible)			
Delirium at baseline	Positive 3D-CAM (limit to incident delirium)			
Auditory/visual impairment prevents study procedures	Per self-report or demonstrated inability during baseline visit (inability to participate)			
Alcohol/substance misuse	CAGE-AID score of 2 or greater (exclude cognitive effects of substances)			
Psychotic disorder	Per self-report or chart (can confound delirium assessment)			
Dementia-level deficits	Per self-report, chart, or TICS < 27 (exclude effects of dementia on delirium assessments)			
Use of a sleep aid	Any prescribed sleep aid being taken at least every other night (potential confound)			
Use of a strong 3A4 inhibitor (per FDA website ⁹²)	Ceritinib, clarithromycin, cobicistat, idelalisib, itraconazole, ketoconazole, nefazodone, nelfinavir, posaconazole, ritonavir, telithromycin, voriconazole (increases drug exposure)			
Intolerance to daridorexant	Per self-report or chart (safety)			
Severe kidney or liver impairment	Child-Pugh score ≥ 7, Cockcroft-Gault < 30 mL/min, or current dialysis (safety)			
Narcolepsy	Per self-report or chart (daridorexant is contraindicated in narcolepsy)			
Prior suicide attempt	Per self-report or chart (package insert indicates a risk of worsening depression or suicidality)			
Suicidal ideation at baseline assessment	Per self-report (package insert indicates a risk of worsening depression or suicidality)			
Any condition that in th study	e opinion of the PI compromises patient safety or data quality if enrolled in the			

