OX2R binding affinity (Ki)	0.93 nM	0.35 nM	2.6 nM			
Major metabolite	None	None	M10			
Effects on QTc	Not clinically relevant	Not clinically relevant	Not clinically			
			relevant			
Mean T _{max}	1-2 hours	2 hours	1-3 hours			
Volume of distribution	31 L	49 L	1970 L			
Terminal t _{1/2}	8 hours	12 hours	17 hours			
Metabolism	CYP3A4 (89%)	CYP3A > CYP2C19	CYP3A4 > CYP3A5			
Severe liver impairment	"Not recommended"	"Not recommended"	"Not recommended"			
Severe renal impairment	50% higher C _{max}	No dose adjustment	50% higher C _{max}			

A.7. A new program of sleep-delirium trials:

This proposed trial is the first in an anticipated research program that aims to combat delirium with sleep interventions. This project builds on the PI's K23 work investigating SWD in relation to delirium and will serve as a transition into translational research to develop sleep-focused delirium therapeutics.

A.8. Whether sleep-focused interventions combat delirium, thus improving long-term cognitive outcomes, is unproven:

SWD are also closely associated with the permanent, progressive conditions of AD and CVD, which cause dementia, and considered a potential mechanism causing or accelerating these conditions, ^{14,70-73} perhaps by way of disrupted glymphatic clearance. ⁷⁴ If (a) delirium mediates the relationship between SWD and AD/CVD and (b) preserving healthy sleep/wake prevents delirium, ^{64,75-77} then preventing delirium could prevent subsequent AD/CVD. ⁷³ What the field needs are conclusive data linking discrete sleep/wake interventions with the prevention of delirium and its dire cognitive and functional outcomes, including ADRD. This project is aligned with the ADRD Milestones as it investigates targets of delirium vulnerability along with longer-term outcomes ⁹ by examining the mechanisms that link delirium physiology with its sequelae. ⁷⁸

A.9. Summary of significance:

Although delirium is an acute event, it often has permanent effects on patients' cognition and function. To date, no medication is FDA-approved to prevent or treat delirium, along with its terrible costs to patients, their families, and health systems.

B. Innovation

B.1. The orexin system invites delirium-related investigation:

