	Study 1	Study 2	mg	mg	mg	mg
	n=309	n=306	Study 1	Study 2	Study 2	Study 2
			n=310	n=308	n=308	n=306
Any AE	105	100	116	117	121	117
	(34%)	(33%)	(38%)	(38%)	(39%)	(38%)
Any SAE	7 (2%)	7 (2%)	3 (1%)	2 (1%)	3 (1%)	3 (1%)
Nasopharyngitis	20 (6%)	16 (5%)	20 (6%)	21 (7%)	13 (4%)	16 (5%)
Headache	12 (4%)	11 (4%)	19 (6%)	16 (5%)	15 (5%)	12 (4%)
Somnolence	6 (2%)	4 (1%)	5 (2%)	11 (4%)	10 (3%)	6 (2%)

Choice of dosing days/times:

We will give 50 mg daridorexant (25 mg to those on moderate 3A4 inhibitor, as above) or placebo 8-10 PM on the first 3 postop nights and evaluate delirium on each of the days following administration—*i.e.*, POD 1–3. We give study agent the night prior to each day's assessment because **the prior night's sleep directly impacts cognition the next day**. Sleep restriction causes neurocognitive impairment the following day with the most pronounced effects in sustained attention (vigilance). We choose 8-10 PM because daridorexant's T_{max} is 1–2 hr. This (1) allows time for its soporific effect and (2) is early enough to mitigate next-morning sedation). S2,67,68 For any subject still intubated during the 8-10 PM window, we will allow for administration up to midnight in the event that they are extubated prior to midnight. This is to maximize the likelihood of administration on the first postoperative night.

Justification and safety information if FDA approved drugs will be administered for non-FDA approved indications or if doses or routes of administration or subject populations are changed:

On September 18, 2024, we received a determination from the US FDA that our proposed trial "meets all meets all of the requirements for exemption from the IND regulations and, therefore, an IND is not required to conduct [this] investigation." See attached document, "FDA exemption determination (24-09-18)."

Medication and matching placebo will be stored by IDS, who will be responsible for randomization subjects to study arms, keeping records on medication storage, and ensuring timely dispensing.

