8. STUDY PROCEDURES

See Table 5 below for the Schedule of Activities

Table 5 - Schedule of activities

Assessment	Screenin	Baseline	PON 1-3	POD 1-3	POD 3-7
	g	(1 hr)	(with	(15 min)	(15 min)
	(15 min)		bedtime		
			meds)		
Verbal consent	X				
CAGE-AID	X				
Written consent		X			
Demographics		X			
CCI		X			
Medication list		X			
Cognition/function					
TICS	X				
MoCA		Full, v8.1			
Lawton		X			
CDR		X			
WTAR		X			
Delirium					
3D-CAM	X			X	Χ [†]
DRS-R98				X	X [†]
Mental health					
PHQ-9		X			
GAD-7		X			
Sleep-related					
PSQI		X			
ESS		X			
RCSQ				X	X [†]
Medication administration			X		
AEs/SAEs					
Questionnaire		X		X	
Chart review*				X	X [†]
Subject to guess whether they received				POD 3	
daridorexant or placebo	 				

Abbreviations: **3D-CAM**, 3-Minute Diagnostic Interview for Confusion Assessment Method; **CAGE-AID**, CAGE [acronym for "Cut-down, Annoyed, Guilt, Eye-opener"] adapted to include drugs; **CCI**, Charlson comorbidity index; **CDR**, Clinical Dementia Rating; **DISH**, Depression Interview and Structured Hamilton; **DRS-R98**, Delirium Rating Scale, Revised 98; **ESS**, Epworth Sleepiness Scale; **GAD-7**, 7-item Generalized Anxiety Disorder scale; **Lawton**, Lawton Instrumental Activities of Daily Living; **MoCA**, Montreal Cognitive Assessment; **PHQ-9**, 9-item Patient Health Questionnaire; **POD**, postoperative day; **PON**, postoperative night (*i.e*, the night of POD 0 [the day of surgery] is defined as PON 1); **PSQI**, Pittsburgh Sleep Quality Index; **RCSQ**, Richards-Campbell Sleep Questionnaire; **TICS**, Telephone Interview for Cognitive Status; **WTAR**, Wechsler Test of Adult Reading

Screening procedures:

As indicated under **7. CONSENT PROCESS** above, consent will involve two steps—a verbal consent for study eligibility screening and, subsequently, signed consent. When obtaining verbal consent, we will

^{*}For evidence of adverse events, documentation of delirium, potential sleep confounds

[†]Daily assessments for delirium and sleep will continue if the subject is delirious on POD 3, until delirium resolves.

Version date: 2/3/2025

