indicate to study prospects that the eligibility questions take 5–10 minutes. We indicate that we keep responses to screening questions, even for those who don't end up taking part, so, as a result and explain that we do not record personally identifying information during the screening process. Before proceeding with the remainder of the eligibility assessment, we also ask the prospective subject to affirm the availability of a study partner should they participate in the study.

Study duration:

Study subjects will participate from the initial screening evaluation prior to surgery, which is usually 1–2 weeks prior to scheduled surgery, through the third postoperative day after surgery (*note*: as in the following paragraph, assessments may be continued past POD 3 if the subject is found to have delirium on POD 3). Most subjects, then, will be enrolled in the study for roughly 2 weeks. However, the duration of study participation will be dependent on the scheduling of preoperative anesthesiology visit in relation to date of surgery.

Choice of POD and assessments for delirium:

We assess delirium on POD 1–3 with the DRS-R-98 as validated based on clinical interview under the supervision of a psychiatrist. We omit delirium assessment on POD 0 because (1) patients are intubated and sedated until the evening of POD 0 and (2) to exclude emergence delirium (*n.b.*, a distinct physiological event due to anesthetic effects¹⁰⁰). With one exception (see below), we restrict delirium assessments to POD 3 because (1) patients are often discharged on POD 3 or 4, (2) postop delirium peaks on POD 2 and 3, coincident with the peak of postop inflammation, ^{101,102} and (3) this allows a commensurate 3-day period across subjects to evaluate for delirium during the days of greatest risk. We use DRS-R-98 as it is well validated and the most robust tool for characterizing delirium phenomenology. ^{1,16,17,20,21,103} Regarding the exception referenced above: to determine delirium duration in all subjects, we continue to perform daily delirium assessments for any subject positive for delirium on POD 3 until no longer positive. Regardless of whether delirium assessments continue beyond POD 3, subjects will still receive study drug for only the first three nights after surgery.

Number of visits:

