6.2 Post-Marketing Experience

The following adverse reactions have been identified during post-approval use of QUVIVIQ. Because these reactions are reported voluntarily from a population of uncertain size, it is not always possible to reliably estimate their frequency or establish a causal relationship to drug exposure.

Psychiatric disorders: Nightmares or abnormal dreams

Immune system disorders: Hypersensitivity (including angioedema, rash, urticaria)

Version date: 2/3/2025

Safety assessments:

In this trial, we obtain demographics and baseline assessment of medical morbidity, medications, cognitive status, and self-report sleep & mental health. Obtaining such information does not entail significant foreseeable risk beyond limited risk of psychological distress or questionnaire fatigue. As we will be completing the 9-question Patient Healthcare Questionnaire (PHQ-9), which assesses suicidal ideation, we have developed a safety plan for anyone who answers positively to question 9 on the PHQ-9 (see Steps taken to minimize risk below).

Adverse event definition:

This is an observational study of medically and surgically ill patients undergoing open-heart surgery, and this population—independent of this study—is at significant risk for a range of medical and surgical complications because of their underlying heart disease, open-heart surgery, and care provided during the perioperative period. In this study, we define an adverse event as any symptom, sign, illness, or experience that develops or worsens during the study that is reasonably attributable to the study assessments or receipt of daridorexant.

Serious adverse event:

A serious adverse event is defined as any adverse event resulting in any of the following:

- Sleep paralysis (inability to move or speak when going to sleep or waking up)
- Cataplexy (discrete episode of muscle weakness, typically associated with strong emotion)
- Complex behaviors while asleep that pose danger to the patient or others (e.g., sexually inappropriate acts)
- Angioedema or anaphylactic reaction to daridorexant
- Death/suicide
- Prolongation of existing hospitalization
- Persistent or significant disability or incapacity
- Medical or surgical intervention required to prevent permanent impairment or damage

Recording adverse events:

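### Table 4's kidney and liver safety limits gate enrolment before surgery, but no rule holds study drug if severe impairment develops before a postoperative dose

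*Protocol*

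**What the plan says.** **The limit.** Table 4 in Section 5 lists severe kidney or liver impairment as an exclusion, defined as "Child-Pugh score ≥ 7, Cockcroft-Gault < 30 mL/min, or current dialysis", and gives safety as the reason.

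**When it is applied.** Section 5 states: "Subjects will be screened in person or by phone for eligibility". Section 8 (Study duration) begins participation there: "Study subjects will participate from the initial screening evaluation prior to surgery", usually one to two weeks ahead. Section 3 allows some patients to be identified in hospital while awaiting surgery, so the interval may be shorter, but the test still comes before surgery. Section 9 (Steps taken to minimize risk) describes the exclusions as a way to avoid recruiting those most at risk.

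**When drug is given.** Section 4.2 gives 50 mg, with "25 mg to those on moderate 3A4 inhibitor, as above) or placebo 8-10 PM on the first 3 postop nights". For a subject still intubated in that window, "we will allow for administration up to midnight in the event that they are extubated prior to midnight".

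**What is looked at after surgery.** Table 5 schedules a chart review on POD 1-3. Its footnote gives the purpose: "For evidence of adverse events, documentation of delirium, potential sleep confounds". Table 5 has no kidney or liver item in any column.

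**Who orders.** Section 9 (Risks pertaining to study participation) makes the treating team responsible for ordering study drug on the three nights. It lists what the team will be taught: the trial, its methods, the need to order, and the reporting of adverse events.

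**The concern.** A numeric safety limit is checked before the event most likely to change the measured quantity, and all drug exposure comes after that event. Section 9 itself describes this population as at significant risk of medical and surgical complications, whether or not they join the study. A subject with adequate kidney function at screening who starts dialysis after surgery would not be eligible for enrolment in that state, yet remains scheduled for every dose still to come.

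Two things are at stake. Safety is a primary outcome (Section 4), and on the dosing nights the protocol leaves its own safety limit to unwritten judgement. The target of Aim 2 is delivery of every dose, and the protocol names no category for a dose properly withheld. The follow-on trial would inherit both features.

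**Working it through.** The protocol states no figure on this point, so there is none to reproduce. The check is to take every provision that could change or stop a dose after surgery and ask whether new organ impairment would trigger it.

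1. **Dose level (Section 4.2).** The only trigger for a change is a moderate CYP3A4 inhibitor, which lowers the dose to 25 mg. The protocol therefore adjusts for one cause of higher exposure, but not for organ impairment arising after surgery.
2. **Timing (Section 4.2).** A subject not extubated by midnight gets no dose that night. This depends on the airway, and kidney or liver function plays no part. The stated aim of the extension is to make a first-night dose more likely.
3. **Early discharge (Section 13).** Drug stops at discharge. This is unrelated to organ function.
4. **Removal (Section 13).** Subjects are removed only for a serious adverse event. In Section 9 that must first be an adverse event, meaning something "that develops or worsens during the study that is reasonably attributable to the study assessments or receipt of daridorexant". New dialysis could meet the seriousness list, but impairment put down to the surgery fails the attribution step. Where the route does apply, it ends in removal; there is no option to hold drug and keep the subject.
5. **Unblinding (Section 9).** This covers emergencies judged potentially attributable to daridorexant, and it ends in withdrawal.
6. **PI-discretion exclusion (Table 4, last row).** It is worded in terms of enrolling the patient, so it acts before dosing.
7. **DSMB (Section 16).** Scheduled reviews follow six and then twelve completers. They cannot act on an individual dose.

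**Order of events.** Table 5 defines PON 1 as the night of the day of surgery.

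| Dose | Scheduled study chart review between surgery and dose | Organ-function purpose stated |
|---|---|---|
| PON 1 | none | – |
| PON 2 | POD 1 | no |
| PON 3 | POD 1, POD 2 | no |

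No provision re-applies the limit. What remains is the treating team's freedom not to order, with no written threshold.

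**Size of exposure.** Each subject receives at most 3 doses. Table 1 lists a 50% higher Cmax for daridorexant in severe renal impairment. Its entry for severe liver impairment is that use is not recommended. The protocol gives no incidence of severe kidney or liver impairment after cardiac surgery, so the expected number of affected subjects cannot be derived.

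**Size of the remedy.** 16 subjects × 3 nights = 48 pre-dose chart checks at most.

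**The case against.** The strongest reply is that Table 4 is an enrolment list and is used as one, so nothing is misstated. These are closely watched inpatients. The treating team orders each dose, routine care is unchanged, subjects are interviewed and records reviewed daily, and the DSMB may recommend new monitoring. Exposure is three doses at most. Much of this stands, and it limits the size of the point. It does not supply the missing rule: the team's education names the need to order and gives no reason to hold.

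A reader might also infer more than the documents support:

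- **That Table 4 and Section 13 contradict each other.** They do not. One governs entry and the other removal; the gap lies between them.
- **That an affected subject must be dosed.** Clinicians may withhold, and Section 13 provides drug for up to three nights. What is missing is the threshold.
- **That impairment present before PON 1 can never reach the serious adverse event route.** The definition includes worsening, so later deterioration could qualify if judged attributable. The pre-PON 1 case is also narrow: the subject must meet a limit, be extubated and be dosed, all on the evening of surgery.
- **That withheld doses could not be told apart from delivery failures.** The protocol does not say this. Ordering and dispensing are separate steps, and reasons may be recorded elsewhere. The protocol simply sets no category.
- **That all of Table 4's limits should be re-scored every night.** This would be unsound. Child-Pugh includes encephalopathy, albumin and clotting. Surgery shifts the last two, and delirium could be scored as encephalopathy, so drug might be held because of the very outcome the programme studies. Cockcroft-Gault assumes a stable creatinine, which is doubtful soon after surgery.

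**Conclusion.** The point holds as a gap in the dosing rule. Followed as written, Section 4.2 schedules 50 mg or placebo (25 mg with a moderate CYP3A4 inhibitor) for a subject who has newly developed the kind of severe kidney or liver impairment that Table 4 excludes for safety. Whether drug is withheld rests on a clinician acting without written guidance. A dose-hold rule belongs in the protocol and is not a detail to leave to a statistical analysis plan.

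The expected harm is modest: a 50% higher Cmax in severe renal impairment over at most three doses. Severe liver impairment is the weightier case, because Table 1 advises against use, but the protocol gives nothing from which to size it. A reader might want the chance that at least one subject is affected. Any such figure would rest wholly on an assumed event rate, so none is given. The conclusion does not depend on one. It rests on reading the listed dosing, removal and unblinding conditions as complete for this protocol.

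The change is worth making now, because it is cheap and the rule would carry into the larger trial.

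**What to change.** In Section 4.2, and as a row in the PON 1-3 column of Table 5, add a pre-dose check of results already in the chart. Hold study drug that night if any of these applies:

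- the subject has started dialysis;
- the latest estimated creatinine clearance is below 30 mL/min, or creatinine is rising fast enough that the clinician judges it so;
- the clinician judges that there is new severe liver impairment.

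Do not re-score the full Child-Pugh each night. Keep the subject in follow-up with all assessments. Record the dose as *held per protocol*, and report such doses separately from delivery failures under Aim 2. Add the rule to the treating-team education in Section 9.

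**Cost.** A protocol amendment of one table row, a short hold rule in Section 4.2 and a line of team education; at most 48 brief chart checks; no new blood tests. The downside is a slightly lower count of doses delivered under Aim 2.

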6. RECRUITMENT METHODS

Study personnel, including the principal investigator and research coordinator, who have routine access to the cardiac surgery clinic and operating room schedules, will pre-screen patients scheduled for SAVR or CABG in direct collaboration with cardiac surgeons and anesthesiology team. A member of the surgery or anesthesiology team will refer eligible study candidates to study personnel (see Referral form). Referred patients will be contacted by study personnel either in person during a scheduled clinic visits or by phone, as feasible.

Version date: 2/3/2025

7. CONSENT PROCESS

Verbal consent:

When contacting study referrals, study personnel will obtain verbal consent to complete a 10-minute assessment to assess study eligibility and document this by signing and keeping on file a copy of the Recruitment Script for that study referral. To confirm eligibility, we will review inclusion and exclusion criteria and screen patients using the Telephone Interview for Cognitive Status (TICS)⁹⁴ and CAGE-Adapted to Include Drugs (CAGE-AID).⁹⁵ As this work ultimately aims to identify an intervention to prevent cognitive impairment, we exclude dementia by chart review (prior diagnosis) and by phone (self-reported diagnosis or TICS < 27 [equivalent to MMSE < 24]). We include mild cognitive impairment (MCI) to increase the likelihood of postoperative delirium occurring in our sample.⁹⁶ These decisions balance the need for homogeneity vs generalizability of our sample.

Signed consent:

Prior to conducting any study procedures, subjects will complete the full informed consent process with research personnel. Research staff will first describe the study to eligible subjects and review the informed consent document. Subjects will then be given as much time to read the consent document as they wish and to ask any questions or discuss any aspect of the study. The subject will be invited to sign the written informed consent form, which will also be signed by research personnel obtaining consent (one copy will be given to the subject and the other copy will be kept under double locked conditions). The consent form includes contact information for study personnel.

Potential subjects for this study will be presumed to have capacity, especially as they have just recently provided consent for anesthesia and heart surgery. However, if the PI has any concerns over whether the subject has the capacity to participate when discussing the study protocol and reviewing what will be required of the subject in this study he will assess capacity. If other trained research personnel are enrolling the subject and has any concerns, he or she will contact the PI (a psychiatrist) who will personally conduct a clinical assessment of decision-making capacity (*i.e.*, communicate a decision of whether to join the study, comprehending the study's purpose, procedures, and potential risks/benefits, appreciate the study's potential impact on recovery, and the ability to make a reasoned decision), either in person or by phone. Patients who lack capacity to consent to study procedures will be excluded from this study, which will limit variance in baseline cognition.

Study partner:

This study protocol requires that subjects have a reliable informant to allow for assessment of cognitive status at baseline. We complete the semi-structured Clinical Dementia Rating (CDR) items with the study partner to ensure we have a good understanding of the subject's memory, problem solving ability, and daily activity. Our conversations with study partners usually take 10–15 minutes and can be either in person or by phone. If the subject develops delirium, their study partner or someone else who is a legally authorized representative will help them decide regarding continued study participation.

Requested Waiver of Documentation for Verbal Consent Process

https://www.rochester.edu/ohsp/documents/ohsp/pdf/policiesAndGuidance/Policy_701_Informed_Consent.pdf

To establish study eligibility, we will be conducting a 10-minute cognitive screen—the Telephone Interview for Cognitive Status (TICS). This will be performed prior to obtaining written consent and enrollment into the study. We will not be recording any personally identifiable information as part of this assessment. We will keep the screening results of individuals screened for eligibility, including TICS results, so we can characterize the broader sample of those referred for study participation. This will also allow us to compare the set of referred individuals who were found to be study ineligible vs study eligible,

which will inform future research in this clinical population. The potential study subject is providing verbal consent for screening, and the brief screen would satisfy criterion 9.1.2 under RSRB policy 701 as "the research presents no more than minimal risk of harm to subjects and involves no procedures for which written consent is normally required outside the research context [45 CFR 46.117(c) and 21 CFR 56.109(c)].

